6.2 ANALYSIS

Patient demographic and clinical characteristics will be summarised using appropriate descriptive statistics. The primary outcome, change in LV/RV ratio before and at 48 hours post baseline will be summarised according to risk group and overall and will be assessed with a two-sided paired t-Test. Linear regression analysis will be used to identify factors, including severity, affecting the change in LV/RV ratio. Survival analysis will be used to model factors affecting mortality. Data will be analysed using R or Stata. An unblinded interim analysis at 100 patients will be performed at 6 month follow up with focus on the primary outcomes. No Stop/Go criteria will be applied as the PE response team decision to treat or not is not protocolised and the study is observational only. A detailed statistical analysis plan will be written with the University of Plymouth Medical Statistics group and finalised before database lock.

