Dendrite	Dendrite clinical systems, electronic research database
Section 251	The purpose of section 251 support is to give the data controller a legal means of providing access to confidential patient information without consent.
SOP	Standard Operating Procedure
SPSS	Statistical Product and Service Solutions (statistical software suite)
UHP	University Hospitals Plymouth NHS Trust
USS	UltraSound Scan
WBC	White Blood Cell

KEY WORDS:

Pulmonary embolism, Thrombectomy.

STUDY SUMMARY

Study Title TiPE

Study Design Prospective observational study to evaluate the use of Computer aided

vacuum thrombectomy (CAVT) within the context of intermediate and

high-risk PE.

Study Participants Patients presenting with intermediate or high-risk PE (as defined by

European Society of Cardiology (ESC) guidelines1) at one of the

participating hospitals.

Eligibility Criteria Study Site Criteria:

1. Availability of 16Fr Penumbra Flash

2. Operational PE Response team

3. Operator experience treating a minimum of 2 previous PE's and experience with Penumbra indigo systems (defined as 3 cases).

Inclusion Criteria Participants:

1. Clinical signs and symptoms consistent with acute PE with duration of 14 days or less

2. Patients who present with CT confirmed PE

3. Defined as intermediate or high-risk PE (according to ESC guidelines¹)

4. Date of CT imaging from within the two-year period

5. Patient is ≥ 18 years of age

6. Informed consent obtained

7. Evidence of cardiac dysfunction (Either biochemical or imaging features of RHS)

Exclusion Criteria:

- 1. Known serious, uncontrolled sensitivity to radiographic agents
- 2. CT not available to evaluate PE
- 3. Low Risk PE as defined by ESC guidelines¹
- 4. Current participation in another investigational drug or device study that may confound the results of this study. Studies requiring extended follow-up for products that were investigational but have since become commercially available are not considered investigational studies
- 5. Other medical, social, or psychological conditions that, in the opinion of the Investigator, precludes the patient from appropriate consent, could limit the patient's ability to participate in the study, including compliance with follow-up requirements, or that could impact the scientific integrity of the study

Planned Sample Size 2000 eligible patients and 200 thrombectomy patients

Follow-up Duration 6 months from date of PE or date of death, whichever is sooner

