2 STUDY OBJECTIVES

2.1 PRIMARY OBJECTIVES

- 1. To evaluate the effectiveness of PE CAVT as a treatment for intermediate and high-risk PE as measured by change pulmonary arterial pressure and in RV/LV (Right Ventricle to Left Ventricle diameter) ratio at 48 (- 24 / + 48) hours post procedure.
- 2. Ascertain the mortality and morbidity profile for CAVT within intermediate and high-risk PE, within 48 (± 12) hours post procedure, 30 (± 7) days, 90 (± 14) days and 6 months (+/- 30 days).

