7.1 DATA FLOW DIAGRAM

7.2 DESCRIPTION OF THE DATA

Sample data points will include the following for **ALL** patients:

Patient demographics

Age, Sex, Medical History, Cancer, Pregnancy, Time of first symptoms, presenting hospital, admission from location (e.g. Own Home/nursing home) transfer in, previous PE, Anticoagulation, Concurrent DVT and Position.

Admission / Diagnosis (at point of diagnosis of PE if not on admission)

Admission observations, Biochemistry including Temperature, BP, Pulse, oxygen saturations and GCS, biochemistry including: WCC, RBC, CRP, GFR and BNP and Troponin

CT findings (including Evidence of RHS parameters including IVC contrast reflux, Septal flattening, clot location, reporter grade)

Base line (Day of referral to PERT if not day of admission)

PESI score, , RV/LV ratio CT, RV/LV ratio USS. Presence of right atrial clot, PFO presence on Echocardiography, eligibility for thrombolysis (e.g. recent head trauma/ ischaemic stroke, previous ICH, Intracranial neoplasm, GI malignancy, GI haemorrhage in previous 21 days, Recent surgery, BP >185, active bleeding, infective endocarditis, Clotting abnormalities), If Thrombolysis given, including dose.

PER Team first assessment including date and time

PER Team initial decision outcome, date and time

PER Team review - Change Decision, date and time - and change in observations and Biochemistry PER Team review - Change Decision 2, date and time - and change in observations and Biochemistry

Discharge

Further procedures, length of stay, (including ICU, HDU, Ward), mortality, Place of discharge to. IVC filter insertion.

Follow up

Day 30 (± 7 days): All cause and PE related Mortality, Local readmission – Patient questionnaire: PEmb-QoL, EQ-5D-5L, Borg Scale

Day 90 (± 14 days): Mortality, Local readmission – Patient questionnaire: PEmb-QoL, EQ-5D-5L, Borg Scale

6 months (+/- 30 days): All cause and PE related Mortality – Patient questionnaire: PEmb-QoL, EQ-5D-5L, Borg Scale

Those undergoing CAVT will have the following additional data collected:

Procedural success and outcome. Procedural time, Access route, Aspiration device used, Separator used, Heparin given, including dose, Concurrent Lysis used, including dose. Thrombectomy time. Pulmonary arterial pressure at start, Pulmonary Arterial pressure at finish. Requiring further procedures, Length of stay, IVC filter insertion, readmission along with:

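### The SAP need only be final by database lock, although an unblinded interim analysis of the primary outcomes comes earlier, so the open details of the primary analysis could be settled after results are seen

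*Protocol*

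**What the plan says.** Section 6.2 states: "A detailed statistical analysis plan will be written with the University of Plymouth Medical Statistics group and finalised before database lock". It also states: "An unblinded interim analysis at 100 patients will be performed at 6 month follow up with focus on the primary outcomes". No stopping rule is attached to the interim: "No Stop/Go criteria will be applied as the PE response team decision to treat or not is not protocolised".

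The planned size in the Study Summary is "2000 eligible patients and 200 thrombectomy patients".

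Part of the primary analysis is already in section 6.2. The change in ventricular ratio (written there as LV/RV) from before to 48 hours "will be summarised according to risk group and overall and will be assessed with a two-sided paired t-Test". Section 2.1 sets effectiveness more widely, "as measured by change pulmonary arterial pressure and in RV/LV (Right Ventricle to Left Ventricle diameter) ratio", and adds a second primary objective on mortality and morbidity.

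The Day 2 echocardiogram and the pressures at the start and end of the procedure fall under the section 7.2 list headed "Those undergoing CAVT will have the following additional data collected". For the baseline ratio, section 7.2 records "RV/LV ratio CT, RV/LV ratio USS".

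**The concern.** Signing the SAP before database lock protects pre-specification only if nobody sees outcome results until lock. Here the protocol plans such a look, on the primary outcomes, part-way through. The final analysis will include the interim patients. Any analysis choice made after the interim can therefore be shaped, knowingly or not, by data that will be used again.

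At stake is whether the final estimate comes from a rule fixed in advance. In a single-cohort before-and-after study there is no randomised or blinded comparison to lean on, so a dated plan is one of the main safeguards. Section 8.4 says the device manufacturer funds the database, site set-up and data collection. That is no sign of a problem, but it gives readers more reason to ask when the plan was fixed.

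**Working it through.** **1. Is sign-off tied to the interim anywhere?** Section 6.2 is the only place that dates the SAP, and the date is database lock. Section 4.5 reviews recruitment at 1 year and 18 months but does not mention the SAP. The order interim, then SAP, then lock is therefore allowed.

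**2. How much data would have been seen?** This depends on who the 100 are, which section 6.2 does not say.
- CAVT patients: 100/200 = 50% of the target.
- All participants: 100/2000 = 5%. At the planned share of 200/2000 = 10%, this is about 10 CAVT patients.

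The first reading is the sensible one, because the Day 2 echo and the procedural pressures exist only for CAVT patients.

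**3. When would it be seen?** Sections 4.1 and 6.1 expect 200 thrombectomies over two years.
- Even accrual: 200/24 = 8.33 per month. The 100th falls at 100/8.33 = month 12, and its 6-month follow-up at month 18. By then 8.33 × 18 = 150 (75%) would be enrolled.
- Unrounded figures: 12 centres × 13 × 2 years × 0.70 = 218.4. The 100th then falls at month 11 and the interim at month 17.
- Section 4.5 limits (90 to 120 thrombectomies in year 1): the 100th falls between 100/120 × 12 = month 10 and 100/90 × 12 = month 13.3. The interim then falls between months 16 and 19.3.

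The planned study period is 30 months, so under even accrual the interim comes about 30 − 18 = 12 months before the planned end.

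**4. What is fixed and what is open?**

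| Item | Position in the protocol |
|---|---|
| Ratio change as outcome, before versus 48 hours | Fixed, 6.2 |
| Two-sided paired t-test, overall and by risk group | Fixed, 6.2 |
| Width of echo window | Fixed: −24/+48 hours in 2.1; −1/+2 days in 7.2 |
| Covariates | Not part of the primary test; used only in the regression in 6.2 |
| Standing of pulmonary arterial pressure | Open: beside the ratio in 2.1; absent from the single primary outcome in 6.2, which then refers to primary outcomes in the plural |
| Baseline ratio | Open: echocardiography in 2.2 Outcomes; CT and ultrasound both recorded in 7.2 |
| Start of the 48 hours | Open: procedure in 2.1; baseline in 6.2, which 7.2 describes as the day of PERT referral if that is not the admission day |
| Missing echoes and early deaths | Not stated |

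Leaving the last item to the SAP is normal. The problem is only that the SAP may come after the look.

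**5. What could late choice do to the error rate? (illustration)** Take two candidate measures with correlation r and no true effect. Let z1 and z2 be the statistics from the first and second halves of the data. Choose the measure with the larger |z1|, then test it on all data with z = √0.5·z1 + √0.5·z2 against 1.96. Results from 2,000,000 simulated studies for each r:

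| r (assumed) | Error, look at 50% | Error, look at 5% |
|---|---|---|
| 0 | 8.2% | 5.4% |
| 0.5 | 7.8% | 5.3% |
| 0.8 | 6.9% | 5.2% |

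Choosing beforehand keeps it at 5%. The documents give neither r nor the number of candidates.

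**6. Is a false positive the likely harm?** The earlier study quoted in section 6.1 gives 0.38/0.27 = 1.41, taking 0.27 as the SD of the change. This agrees with the protocol's statement of d above 1. The expected z for a paired test is d√n. With n = 200 it is 14.1 at d = 1, 7.1 at d = 0.5 and 2.8 at d = 0.2. Unless the effect is near the 0.2 named in section 6.1, the test rejects under almost any definition. Late choice would then act mainly on the size of the reported change.

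**The case against.** The strongest reply is that the outcome, contrast and test are already named, so little is left to choose. That stands for the items marked fixed in the table. A reader might infer that the whole primary analysis can be rewritten after the interim. The documents do not support this, since changing those items would depart from the protocol itself. The echo window and covariates do not belong on the open list either.

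Second, lock is a latest date, and the SAP is not at hand. It may be signed well before the interim. This also stands: the protocol lacks a safeguard, but it does not plan a breach.

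Third, there are no randomised arms and no stop/go rule, so no alpha is spent on an early claim. That is correct, and it removes the usual group-sequential concern. It does not remove data-driven choice among analyses.

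Fourth, the conflicts over pressure, baseline modality and the start of the 48 hours are in the protocol and would survive a change of SAP date. That is partly true. They still have to be resolved somewhere, and the date decides whether this happens before or after results are known.

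**Conclusion.** The concern holds in a limited form. The stated deadline allows the unsettled parts of the primary analysis to be decided after an unblinded look at the primary outcomes. It should be corrected, but it does not invalidate the design.

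The size is conditional. The 50% figure requires the 100 to be CAVT patients. If they are all participants, the look covers about 10 CAVT patients and the effect on error is negligible. The month-18 date assumes even accrual, with a range of 16 to 19.3 under the section 4.5 limits.

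A reader might take the error rates as this study's false-positive risk, or raise them by assuming more candidate definitions. The documents do not support either step. The 7% to 8% describes one assumed selection rule under no effect, whereas the protocol expects a real effect. The harm to guard against is an estimate chosen because it looked favourable.

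**What to change.** In section 6.2, move the SAP deadline from database lock to the interim. Suggested wording: the SAP will be final, signed and dated before any data are extracted for the interim analysis; the interim will follow that version; any later change will be listed and reported as made after the interim.

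In the same section, state that the interim covers the first 100 CAVT participants with 6 months of follow-up.

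The signed SAP should settle the standing of pulmonary arterial pressure, the modality of the baseline ratio, the start of the 48 hours, and the handling of missing echoes and early deaths. Sections 2.1, 2.2 Outcomes, 6.2 and 7.2 should be brought into line with it.

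The cost is that SAP writing moves forward, by up to about a year under even accrual. Sample size, power and data collection do not change. Once the interim has been run, the safeguard cannot be restored for those 100 patients.

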7 DATA MANAGEMENT AND DATA SHARING PLAN

To comply with the Data Protection legislation information will be collected and used fairly, stored safely and not disclosed to any unauthorised person. This applies to both manual and electronically held data.

[figure not shown]
The Chief Investigator will preserve the confidentiality of participants taking part in the study and ensure the UK General Data Protection Regulation (GDPR) in conjunction with the UK Data Protection

Act 2018, which sets out the statutory requirements for the processing of personal data, is adhered to.

7.1 DATA FLOW DIAGRAM

7.2 DESCRIPTION OF THE DATA

Sample data points will include the following for **ALL** patients:

Patient demographics

Age, Sex, Medical History, Cancer, Pregnancy, Time of first symptoms, presenting hospital, admission from location (e.g. Own Home/nursing home) transfer in, previous PE, Anticoagulation, Concurrent DVT and Position.

Admission / Diagnosis (at point of diagnosis of PE if not on admission)

Admission observations, Biochemistry including Temperature, BP, Pulse, oxygen saturations and GCS, biochemistry including: WCC, RBC, CRP, GFR and BNP and Troponin

CT findings (including Evidence of RHS parameters including IVC contrast reflux, Septal flattening, clot location, reporter grade)

Base line (Day of referral to PERT if not day of admission)

PESI score, , RV/LV ratio CT, RV/LV ratio USS. Presence of right atrial clot, PFO presence on Echocardiography, eligibility for thrombolysis (e.g. recent head trauma/ ischaemic stroke, previous ICH, Intracranial neoplasm, GI malignancy, GI haemorrhage in previous 21 days, Recent surgery, BP >185, active bleeding, infective endocarditis, Clotting abnormalities), If Thrombolysis given, including dose.

PER Team first assessment including date and time

PER Team initial decision outcome, date and time

PER Team review - Change Decision, date and time - and change in observations and Biochemistry PER Team review - Change Decision 2, date and time - and change in observations and Biochemistry

Discharge

Further procedures, length of stay, (including ICU, HDU, Ward), mortality, Place of discharge to. IVC filter insertion.

Follow up

Day 30 (± 7 days): All cause and PE related Mortality, Local readmission – Patient questionnaire: PEmb-QoL, EQ-5D-5L, Borg Scale

Day 90 (± 14 days): Mortality, Local readmission – Patient questionnaire: PEmb-QoL, EQ-5D-5L, Borg Scale

6 months (+/- 30 days): All cause and PE related Mortality – Patient questionnaire: PEmb-QoL, EQ-5D-5L, Borg Scale

Those undergoing CAVT will have the following additional data collected:

Procedural success and outcome. Procedural time, Access route, Aspiration device used, Separator used, Heparin given, including dose, Concurrent Lysis used, including dose. Thrombectomy time. Pulmonary arterial pressure at start, Pulmonary Arterial pressure at finish. Requiring further procedures, Length of stay, IVC filter insertion, readmission along with:

Day 1 – Observations, including Temperature, BP, Pulse, oxygen saturations and GCS, biochemistry including: WCC, RBC, CRP, GFR and BNP and Troponin (if available)

Day 2 (+ 2 days / - 1 days) – Observations, including Temperature, BP, Pulse, oxygen saturations and GCS (if available). Echocardiogram with LV/RV ratio

Day 3 – Observations, including Temperature, BP, Pulse, oxygen saturations and GCS, biochemistry including: WCC, RBC, CRP, GFR and BNP and Troponin (if available) Day 5 – Observations, including Temperature, BP, Pulse, oxygen saturations and GCS, biochemistry including: WCC, RBC, CRP, GFR and BNP and Troponin (if available)

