- 7. Evidence of cardiac dysfunction (Either biochemical or imaging features of RHS)

Inclusion criteria Operator:

 Operator experience treating a minimum of 2 previous PE's and experience with Penumbra indigo systems (defined as 3 cases).

Screening for eligibility

Exclusion criteria:

- Known serious, uncontrolled sensitivity to radiographic agents
- 2. CT not available to evaluate PE
- 3. Low Risk PE as per ESC guidelines¹
- 4. Current participation in another investigational study that may confound
- 5. Other medical, social, or psychological conditions that, in the opinion of the Investigator, precludes the patient from appropriate consent, could limit the patient's ability to participate in the study.

Exclusion

Patient choice

Data collection

Data on patients regarding patient demographics, physiological parameters, PESI score, CT findings, clinical status, procedural information, day 1,3,5 observations, length of stay, readmission rates, further procedures and outcome at 30 days, 90 days and 6months.

Final cohort for analysis

Full cohort analysis will be performed on anonymised data set.

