2.2 OUTCOMES

Effectiveness of CAVT will be determined by the change in RV/LV ratio on Echocardiography and the reduction in direct invasive measurement of the Pulmonary artery pressure at the beginning and end of the procedure.

Technical success will be determined by the operator comparing pre and post imaging and pulmonary artery pressures. Morbidity and mortality will be expressed as percentage of the cohort. Imaging features, service design, PERT team decision and comorbidities effect on outcomes will be assessed via regression analysis.

The service design and effect on thrombectomy will be assess by service questionnaire at site set up describing the service design factors. Patient reported outcomes like quality of life and breathlessness will be assessed to determine improvement as per their validated questionnaires.

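### Primary objective 2 runs morbidity to 6 months, but the scheduled readmission item stops at day 90 and section 7.2 limits it to local readmission

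*Protocol*

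**What the plan says.** Protocol 2.1, primary objective 2: "Ascertain the mortality and morbidity profile for CAVT within intermediate and high-risk PE", at 48 hours, 30 days, "90 (± 14) days and 6 months (+/- 30 days"). Section 2.2 Outcomes adds that "Morbidity and mortality will be expressed as percentage of the cohort"; the protocol does not list which events make up morbidity.

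The data collection box of the study flow chart names "length of stay, readmission rates, further procedures and outcome at 30 days, 90 days and 6months".

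Section 7.2, follow-up for all patients, has three lines:
- "Day 30 (± 7 days): All cause and PE related Mortality, Local readmission", plus questionnaires
- "Day 90 (± 14 days): Mortality, Local readmission", plus questionnaires
- "6 months (+/- 30 days): All cause and PE related Mortality", plus questionnaires, with no readmission item

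Appendix 1, table for all participants, marks readmission at 30 and 90 days and leaves the 6-month cell empty. That row carries no restriction to local readmission. The extra CAVT items in 7.2 name readmission once more, with no time point and no such restriction.

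Section 5.2 has the investigator look for device and procedure adverse events at 30 days, 90 days and 6 months. Relevant events are collected until 6 months after the index procedure.

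**The concern.** A primary objective and the flow chart reach to 6 months, while the two places that tell sites what to collect stop this item at day 90. Apart from death, readmission is the only hospital event that the schedule collects after discharge in every participant. A site that follows the schedule has nowhere to enter, for example, a recurrent PE or an anticoagulant bleed that brings a non-CAVT patient back in month 5.

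The restriction to local readmission adds a second loss that applies from discharge onward. The protocol expects some patients to arrive from elsewhere, since it records presenting hospital and transfer in, and a return to another hospital may not count as local.

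At stake is the readmission part of the 6-month morbidity profile, and with it any use of readmission for the comparison of hospitals (secondary objective 6) or for resource use (secondary objective 14). A later analysis plan can define the endpoint but cannot supply events that nobody recorded.

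**Working it through.** The protocol states no readmission rate, so there is no figure to reproduce. The check compares the relevant places, then illustrates the possible size.

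**Side by side**

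| Place | 30 days | 90 days | 6 months |
|---|---|---|---|
| 2.1, primary objective 2 (morbidity) | yes | yes | yes |
| Flow chart (readmission listed with outcomes) | yes | yes | yes, on the natural reading |
| 7.2, follow-up (readmission) | local only | local only | none |
| Appendix 1, all participants (readmission) | yes | yes | none |
| 5.2 (device and procedure events, CAVT) | yes | yes | yes |

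**What other sections recover**
- CAVT patients: a late readmission caused by the device or procedure falls under 5.2. Section 5.2 also says SAEs are recorded, and 5.1 makes hospitalisation a seriousness criterion. But 5.1 limits SAEs to unexpected events, and 5.2 limits adverse event recording to CAVT and the relevant procedure. A late readmission not attributed to CAVT therefore has no assured place.
- Non-CAVT patients: the event window in 5.2 is counted from the procedure, so nothing there covers their readmissions after day 90.
- Questionnaires at 6 months measure quality of life and breathlessness, not hospital events.

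**Time without the item** (6 months taken as 183 days)
- Nominal: 183 − 90 = 93 days; 93/183 = 51%.
- Shortest gap within the windows: 90 + 14 = 104 and 183 − 30 = 153; 153 − 104 = 49 days; 49/153 = 32%.
- Longest gap: 90 − 14 = 76 and 183 + 30 = 213; 213 − 76 = 137 days; 137/213 = 64%.

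These are shares of calendar time. They equal the share of events lost only if readmissions are spread evenly over follow-up.

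**Illustration of events lost** (all inputs assumed; the protocol gives none)
- f = share of 6-month readmissions that occur by day 90, from 0.5 (about an even spread) to 0.8.
- L = share of those that are local, from 0.5 to 1.0.
- Share captured = f × L. Lowest: 0.5 × 0.5 = 25%. Highest: 0.8 × 1.0 = 80%.
- With L = 1.0, the day-90 cut-off alone loses 1 − 0.8 = 20% to 1 − 0.5 = 50%.
- For an assumed true rate of 20% in 200 CAVT patients, one readmission each: 200 × 0.20 = 40 patients. Seen: 40 × 0.25 = 10 (5%) to 40 × 0.80 = 32 (16%).

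The illustration concerns the scheduled item only. Events picked up through 5.2 in CAVT patients would reduce the loss in that group.

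**The case against.** The strongest reply is that readmission is not morbidity. Primary objective 2 concerns CAVT patients, and for them 5.2 follows device and procedure events and SAEs to 6 months; three patient-reported measures are also taken at 6 months. This stands, and it narrows the gap to the readmissions named in the verdict. It does not close it.

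The second reply is that the protocol is inconsistent rather than silent. Section 7.2 opens with "Sample data points will include the following for" all patients, so the list need not be complete, and the CAVT items repeat readmission without a time or a local limit. This is fair. But Appendix 1, which sites work from, omits the same 6-month cell. An inconsistency over what to collect still has to be settled before the 6-month contacts.

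Two stronger readings are tempting and not supported:
- *Transferred patients are readmitted elsewhere, so CAVT and receiving centres look better than they are.* The protocol gives no transfer or out-of-area readmission rates and does not define local. Any numerical example must assume the difference it then shows. The bias could also run the other way, since CAVT patients have extra event follow-up and an unrestricted readmission item. No objective compares readmission between CAVT and non-CAVT patients; that comparison is stated only for dyspnoea and quality of life.
- *The blank readmission row in the CAVT-only table shows that CAVT patients have no readmission follow-up.* That table ends at discharge, so the row could not be filled. Their later follow-up is in the all-participants table.

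**Conclusion.** The point holds as a mismatch between a primary objective and the collection schedule. If 7.2 and Appendix 1 are followed, three groups of events have no assured record: readmissions after day 90 in CAVT patients that are not attributed to CAVT, all readmissions after day 90 in non-CAVT patients, and readmissions to other hospitals at any time if the local limit in 7.2 applies. A 6-month readmission rate built on the scheduled item would be too low.

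The direction for that rate follows from the documents; the size does not. The 25% to 80% range rests wholly on the assumed f and L. A reader might infer that the nominal 51% of follow-up means half of readmissions are lost, or that 6-month morbidity as a whole is missed. Neither follows: the first is calendar time, and the second ignores 5.2. Whether the loss differs by transfer status, centre or CAVT use cannot be derived from the protocol. Recording transfer in would allow a later look at this, but would not bring back unrecorded readmissions.

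**What to change.** Reconcile the flow chart, 2.1, 7.2 and Appendix 1:
- In 7.2 and the all-participants table of Appendix 1, add readmission at 6 months for all participants.
- In 7.2, replace the local item by *readmission to any hospital since last contact (date, reason)* at 30 days, 90 days and 6 months, and use the same wording in Appendix 1.
- Collect it as one item in the Dendrite questionnaire already sent at these three times, and in the nurse call to those who do not complete it (7.4). Use site records as the second source, including for patients who have died and cannot report.

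The cost is one question at three existing contacts and a table correction. The downside is that readmissions elsewhere would be self-reported, so dates and reasons are less exact. Patients who lose capacity stay uncovered from that time, because 4.3 ends their data collection; their number should be shown beside the rate.
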